7.4.3 Radiocopper Packaging and Labelling

The labelling of the radiocopper ready-to-use solution for clinical use will comply with the applicable (local) laws and regulations.

Protocol VTX-801_CLN_001	Investigational Product: VTX-801
	Version: 9 dated 07 AUG 2023
	Author: Aixial Group CRO

7.4.4 Radiocopper Dosage, Preparation and Administration

During the study, each patient will receive on 3 separate occasions one intravenous administration of █ MBq ($\pm 10\%$) radiocopper.

Administration of radiocopper will take place under the supervision of an Investigator or designee. Before administration of the bolus, 10 mL of sterile sodium chloride solution (0.90% w/v of NaCl) will be injected to confirm that the intravenous access is intact. After administration of the bolus, the intravenous access will be flushed with 10 mL of the same solution. The Investigator or designee will check for extravasation (i.e. using a gamma camera or handheld probe) after each radiocopper injection.

The time of administration of radiocopper will be recorded in the source data and eCRF.

7.4.5 Radiocopper Storage, Disposal and Accountability

Upon receipt of the radiocopper, the responsible person will inspect the shipment and return the enclosed acknowledgement of receipt form duly completed and signed (date/time point of receipt must be noted).

In accordance with applicable local Radiation Protection Regulations, the study site is responsible for all radiocopper received, processed, stored and disposed. Sites' trained personnel will be responsible for storage in a locked container in the 'hot room' (a restricted access room) according to instructions provided by manufacturer. Only trained personnel will handle the radiocopper.

After decay below the legal limit, all unused material radiocopper and packaging must be disposed by the site according to its standard operating procedure (SOP) on nuclear waste.

The sites' trained personnel will be responsible for the inventory and accountability of radiocopper.

7.5 Immunosuppressive Regimens

All treatments given as part of the immunosuppressive (IS) regimen will be supplied and reconciled by the study site in accordance with their local dispensing and accountability procedures. The products should be stored, handled and prepared in accordance with

Protocol VTX-801_CLN_001	Investigational Product: VTX-801
	Version: 9 dated 07 AUG 2023
	Author: Aixial Group CRO

the manufacturer's instructions. The Investigator will record patient compliance with the IS regimen in the eCRF.

7.5.1 Prophylaxis of IARs, Immune T-cell Response Against the AAV Capsid and

In order to prevent potential IARs that may occur during or within 24 hours post-VTX-801 infusion, a single injection of 100 mg of methylprednisolone will be administered intravenously prior to any VTX-801 infusion (see Section 7.2.5.1).

Based upon recent published experience in AAV-based gene therapy trials, mitigation of the immune T-cell response against the AAV vector capsid will include oral steroid (prednisone or prednisolone) prophylaxis. Furthermore, Sirolimus will be added in order to improve such immune modulation regimen. Such a regimen may be useful to optimally mitigate the above effects, especially in the context of a liver disorder that may be more susceptible to developing reactions to hepatic viral infections. The rationale to use Sirolimus in this setting is the known effect on regulatory T-cells, which are essential to establish and maintain immune tolerance. Of interest, tacrolimus is currently used in a hemophilia AAV-based gene therapy (IV route) trial for the same purpose (ClinicalTrials.gov Identifier: NCT03369444). Furthermore, Sirolimus in combination with methylprednisolone and rituximab has also been safely co-administered with an AAV4 vector in a phase I/II trial of intra-diaphragmatic gene transfer in children affected by Pompe disease (Corti et al, 2014). Mammalian target of rapamycin (mTOR) inhibitors have been shown to be effective and safe in adults and children following solid organ transplantation. Interestingly, prospective and retrospective data in pediatric patients (the most fragile population in this field) converted from calcineurin inhibitor therapy to mTOR inhibition suggest preservation of Immunomodulatory efficacy without adding significant risk of side effects (Ganschow et al, 2013).

The IS regimen should be administered according to the protocol below, in line with drug labels.

- **Prevention of hypersensitivity reactions:**

- **Methylprednisolone** 100 mg will be administered IV one hour before the VTX-801 infusion.

- **Prevention of T-cell immune response against AAV capsid:**

Protocol VTX-801_CLN_001	Investigational Product: VTX-801
	Version: 9 dated 07 AUG 2023
	Author: Aixial Group CRO

Protocol VTX-801_CLN_001	Investigational Product: VTX-801
	Version: 9 dated 07 AUG 2023
	Author: Aixial Group CRO

- **Oral steroid (Prednisone or Prednisolone)** 60 mg/day administered orally for one week starting the day after VTX-801 administration according to Table 6 and stopped at the end of Week 8 (8 weeks in total).

The tapering course of steroid treatment has been chosen to prevent the development of hypothalamic pituitary adrenal (HPA) suppression; the Investigator should nevertheless keep in mind the possible need for stress steroid coverage for any stress situation (e.g. infection, surgery) around or after steroid treatment.

Table 6 Dose Tapering for Oral Steroid

Week number	Oral steroid (Prednisone or Prednisolone) dose
Week 1, from Day 2 (6 days in total)	60 mg, oral
Week 2	40 mg, oral
Week 3	20 mg, oral
Week 4	10 mg, oral
Week 5	10 mg, oral
Week 6	10 mg, oral
Week 7	5 mg, oral
Week 8	5 mg, oral
Week 9	Stop

- History of depression is frequent in WD patients; particular care is required when considering the use of systemic corticosteroids in patients with existing or previous history of severe affective disorders in themselves or in their first-degree relatives. These would include depressive or manic-depressive illness and previous steroid psychosis.

Protocol VTX-801_CLN_001	Investigational Product: VTX-801
	Version: 9 dated 07 AUG 2023
	Author: Aixial Group CRO

[REDACTED]. DMC data monitoring will continue and the committee will be informed should any adverse events of interest, especially ALT increases, occur after the end of the IS regimen; therefore, the most up-to-date safety information will be taken into account in the DMC evaluation and recommendation for dose escalation at the next dose level (cf. DMC Charter).

Protocol VTX-801_CLN_001	Investigational Product: VTX-801
	Version: 9 dated 07 AUG 2023
	Author: Aixial Group CRO

7.5.2 Mitigation of Overt Transaminase Increase

7.5.2.1 Surveillance of transaminase increase

During the post-administration follow-up period, each patient will follow a comprehensive surveillance plan monitoring liver biochemistry, including ALT. Instances of ALT $\geq 1.5 \times$ baseline (in any laboratory in charge of analysis) up to 9 months post-VTX-801 infusion should be reported to the Sponsor within 24 hours of the laboratory value being available; reporting is via data entry into the clinical trial database. Laboratory alerts will also be put in place where possible. Due to the unknown timing of the potential rise in hepatic transaminases, unscheduled visits and blood/urine samples may be necessary to evaluate safety and/or potential or suspected loss of efficacy.

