7.5.2.2 Reporting, management and search for etiology of transaminase increase

In case an ALT increase $\geq 1.5 \times$ baseline is observed between Week 2 and Month 9 post-VTX-801 administration, and **within 24 hours of awareness**, the Investigator will enter the AE into the eCRF and discuss with the Sponsor medical monitor (or delegate) the appropriateness of initiating reactive steroid treatment.

If the above-mentioned transaminase increase is ALT or AST $\geq 5 \times$ ULN (consistent with suspected DILI criteria listed in Section 6.3), a DILI form will be completed and reported as outlined in Section 9.6. A liver biopsy will be performed as soon as possible (if possible, within 24-48 hours), in order to assess the results of the liver biopsy and the respective transaminase elevation for causality through HAC adjudication; furthermore, testing of liver biochemistry should be repeated within 48 to 72 hours to confirm the abnormalities and the patient should be placed in close monitoring and followed until normalization or stabilization. *Note that DILIs will be evaluated as per current guidelines: Clinical Practice Guidelines: Drug-induced liver injury, EASL, 2019 and Guidance for Industry Drug-Induced Liver Injury: Premarketing Clinical Evaluation, FDA guideline, 2009.*

If the decision is taken to initiate reactive steroid treatment:

- An unscheduled sampling for IFN-gamma ELISpot to AAV3B capsid and miniATP7B transgene assays will be taken, ideally before steroid reactive treatment initiation.

Protocol VTX-801_CLN_001	Investigational Product: VTX-801
	Version: 9 dated 07 AUG 2023
	Author: Aixial Group CRO

- The investigator will perform the evaluation for an alternative etiology for liver disease (other than T-cell immune response to VTX-801), including:
 - o acute viral hepatitis (immediate testing):
 - PCR for HSV, CMV, EBV, HCV
 - serology for HAV: HAV IgM
 - HBV testing: HBsAg and if positive HBV DNA
 - serology for HEV (IgG and IgM) and HEV RNA
 - o alcoholic and autoimmune hepatitis: ANA, SMA, and anti-LKM1 auto-antibodies, as well as total IgG testing,
 - o hepatobiliary disorders other than WD,
 - o cardiovascular causes,
 - o concomitant treatments.

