Abbreviations: ATP7B= Copper-transporting P-type ATPase; ALP= ALkaline Phosphatase; ALT= ALanine aminoTransferase; aPTT= activated Partial Thromboplastin Time; AST= ASpartate aminoTransferase; BUN= Blood Urea Nitrogen; CBC= Complete Blood Count, GGT= Gamma-Glutamyl Transpeptidase; HBC= Hepatitis B Core antibody; HBS antigen= Hepatitis B Surface antigen; HCV= Hepatitis C Virus; HIV= Human Immunodeficiency Virus; HTLV= Human T-cell Lymphotropic Virus; INR= International Normalized Ratio; LDH= Lactate DeHydrogenase; LDL= Low-Density Lipoprotein; RBC= Red Blood Cell; RNA= RiboNucleic Acid; WBC White Blood Cell

In relation to the Sirolimus treatment, patients will be monitored for hyperlipidemia. A lipid panel consisting of low-density lipoprotein (LDL), high-density lipoprotein (HDL),

Protocol VTX-801_CLN_001	Investigational Product: VTX-801
	Version: 9 dated 07 AUG 2023
	Author: Aixial Group CRO

triglycerides and total cholesterol is included at Screening 1, Screening 2, Week 4 and Week 8.

Each patient will have a comprehensive surveillance plan which monitors liver enzymes and liver function tests post administration of VTX-801. It will include a test at each visit occurring either on site or at home (home nurse) and twice a week sampling between Week 4 and Week 12. Additionally, availability of laboratory results will be optimized in order to ensure quick Investigator accessibility to the results (less than 3 days) to make a decision on further action.

Furthermore, reports of abnormal ALT (defined as $\geq 1.5 \times$ baseline) will also be made available to Sponsor within 24 hours of the laboratory value being available (cf. Section 7.5.2).

Remnant blood and urine samples may be used for future biomarker explorations (excluding any genotyping) as data emerges; this will be the subject of an optional approval by patients in the informed consent (tick box).

Table 8 outlines the frequency of sampling of liver biochemistry parameters after VTX-801 administration, including both locally and centrally analyzed samples.

Protocol VTX-801_CLN_001	Investigational Product: VTX-801
	Version: 9 dated 07 AUG 2023
	Author: Aixial Group CRO

Table 9 Sampling Frequency of Liver Biochemistry Panel Following VTX-801 Administration

Period	Frequency
Weeks 1 to 3	Once a week
Weeks 4 to 12	Twice a week
Weeks 13 to 16	About Weekly, except for week 14
From Week 20 till End of Year 1	About monthly
Year 2	Every 3 months
Years 3-5	Every 6 months

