9.3.2 Reporting of Serious Adverse Events and Adverse Events of Special Interest

Any SAE meeting the criteria described in Section [9.2.6 \(Table 15\)](#), any AESI meeting the definitions in Section [9.6](#), or any event applicable to the study Stopping Rules must be **entered into the eCRF within 24 hours of first awareness** of the event by study personnel. A causality assessment must be provided at the time of reporting and a

Protocol VTX-801_CLN_001	Investigational Product: VTX-801
	Version: 9 dated 07 AUG 2023
	Author: Aixial Group CRO

narrative should also be provided. Any SAEs experienced after the 5-Year follow up period should be reported to the designated CRO designee safety group if the Investigator has assessed that the SAE is possibly, probably or definitely related to IMP administration.

Entry of an SAE/AESI (or updated SAE/AESI information) into the eCRF will trigger an automatic alert to the designated CRO Safety group (Aixial).

If the EDC system is **not available**, SAEs/AESIs should be reported by emailing or faxing a completed paper SAE/AESI Report Form to the designated CRO safety group within 24 hours of site awareness. The SAE/AESI may be reported by telephone; however, this must be followed up within 24 hours with either a completed paper SAE/AESI Report Form (if EDC system is still not available) or by recording it into the eCRF (if EDC becomes available in the meantime). Additionally, it may be necessary for the designated CRO safety group to communicate with the Investigator if additional information is required. Note: when EDC becomes available, the SAE/AESI Report must still be entered in the eCRF despite the paper SAE Form being submitted.

During both business and non-business hours, the email address, telephone and fax numbers listed below can be used to notify the designated CRO safety group. If a paper SAE/AESI Report Form is submitted via email or fax and no acknowledgement is received within one working day, the report should be re-submitted.

Reportable Events Hotline:
Aixial Group CRO (formerly Cmed)
Email: [REDACTED] [REDACTED] [REDACTED] [REDACTED] [REDACTED]

All additional follow-up evaluations must be reported within 24 hours of site awareness, following the same processes. The Sponsor is responsible for complying with applicable regulatory reporting requirements for SAEs and, where necessary, for ensuring the relevant authorities are notified (see Section 9.4). The Investigator will ensure the

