9.6 Adverse Event of Special Interest

A serious or non-serious event of scientific and medical concern specific to a Vivet Therapeutics' product or program, for which ongoing monitoring and rapid communication by the Investigator to the Sponsor and CRO can be appropriate. Such an event might warrant further investigation in order to characterize and understand it.

AESIs are reportable to the designated Aixial DSPV group from the time of VTX-801 administration regardless of seriousness or causality. Upon receipt, these AEs will be captured in the safety database, targeted follow-up queries will be sent to sites, and source documentation will be sent to the DMC and / or HAC (as outlined in the respective study committee charters).

The AESIs for this study (defined at any timepoint in the study after VTX-801 administration) are:

- DILI as defined in Section [6.3](#).
- ALT \geq 1.5 x Baseline.
- Neurological, psychiatric or behavioral AEs (either new or worsening from baseline).
- Copper deficiency as defined in Section [9.7](#).
- CTCAE Grade 3 or 4 AEs triggering stopping criteria (defined in Section [6.3](#)).

Protocol VTX-801_CLN_001	Investigational Product: VTX-801
	Version: 9 dated 07 AUG 2023
	Author: Aixial Group CRO

- Newly diagnosed malignancy after VTX-801 administration if not reported as SAE (see Section 6.3).
- Biochemical deterioration after WD background treatment withdrawal (see Section 4.6).
- Other events identified in medical review of special interest as agreed by the Sponsor medical monitor.

Any confirmed or suspected AESIs will be closely monitored by the Investigator and reported to the designated CRO and Vivet following the same procedure as for SAEs, as described in Section 9.3.2.

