10.5.3 Visit 10 (Week 4 ± 2 days)

Importantly, from Week 4 to Week 12 inclusive post VTX-801 administration, liver function tests will be performed twice a week.

Additionally, in the case that an ALT increase $\geq 1.5 \times$ baseline between Week 4 and Month 6 post-VTX-801 administration occurs despite the immunosuppressive regimen (Section 7.5), site has to specifically refer to Section 7.5.2 for guidance.

Protocol VTX-801_CLN_001	Investigational Product: VTX-801
	Version: 9 dated 07 AUG 2023
	Author: Aixial Group CRO

Refer to Table 2 Summary of Schedule of Events: Baseline to Week 12				
Visit 10	Week 4 ± 2 days	Follow-up	Outpatient visit	Cross-reference
Vital signs				Section 8.1.4
Physical examination				Section 8.1.3
Alcohol consumption				Section 7.7
Central Laboratory: Blood/urine biochemistry with lipid panel; hematology; coagulation Fasting conditions are required for the lipid panel.				Section 8.1.11
Central Laboratory: Liver biochemistry panel				Section 8.1.11
Local laboratory: Liver biochemistry panel				Section 8.1.12
Ceruloplasmin (enzymatic assay and nephelometry), total Cu, REC, RAC, CuEXC, ANCC, CRP				Section 8.1.13
Anti-AAV3B capsid neutralizing antibodies				Section 8.2.1
Vector shedding: blood, urine, saliva, feces - mandatory Note: at all visits until end of year 1, as applicable, vector shedding sampling is to occur at every site scheduled visit until 3 consecutive concerned samples are negative (at or below quantification limit)				Section 8.2.3
ELISA and IFN-gamma ELISpot				Section 8.2.4
Sirolimus				Section 7.5
Sirolimus level test: sampling for blood trough concentration 28 days after starting treatment with Sirolimus				Section 7.5
Oral steroid (Prednisone or Prednisolone)				Section 7.5.1

Protocol VTX-801_CLN_001	Investigational Product: VTX-801
	Version: 9 dated 07 AUG 2023
	Author: Aixial Group CRO

Adverse events	Section 9.2
Concomitant medications	Section 8.1.2

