7.9.1 Adverse Events

Adverse events (AEs) will be coded using MedDRA dictionary.

AEs will be graded according to the National Cancer Institute – Common Terminology Criteria for Adverse Events (NCI-CTCAE) version 5, based on study protocol.

The following definitions will be used:

- Treatment-emergent AEs (TEAEs): AEs that occurred during on-treatment period, from the day of VTX-801 dosing,
- Related AEs: AEs suspected by the Investigator to have a relationship to study treatment (as recorded on the AE eCRF page, Relationship to VTX-801 = Possibly related, Probably related, Definitely related or missing,
- Serious Adverse Events (SAE): serious AEs (as recorded on the AE eCRF page, Does AE Meet the Definition of an SAE = Yes),
- AEs leading to Death: adverse event leading to death (as recorded on the AE eCRF page, Results in death, or Outcome = Fatal, or Grade = 5),
- Liver function AEs: adverse event meeting the definition of a suspected DILI (as recorded on the AE eCRF page, does AE meet the definition of a suspected DILI event? = Yes).

An overview summary table will present the number and percentage of patients with a TEAE, including:

- TEAEs / TEAEs related to study treatment,
- Serious TEAEs / Serious TEAEs related to study treatment,
- Liver TEAEs / Liver TEAEs related to study treatment,

- Adverse events of special interest (AESI) / AESI related to study treatment,
- Dose Limiting Toxicity / Dose Limiting Toxicity related to study treatment,
- TEAEs leading to death / TEAEs related to study treatment leading to death,
- TEAEs with NCI-CTCAE grade ≥ 3 / TEAEs related to study treatment with NCI-CTCAE grade ≥ 3 ,
- TEAE meeting any stopping rule,
- TEAE Related to Radiocopper Administration,
- TEAE related to Other Study Procedure.

In addition, the following tables will be produced by SOC and PT:

- TEAEs / TEAEs related to study treatment,
- Serious TEAEs / Serious TEAEs related to study treatment,
- Liver TEAEs / Liver TEAEs related to study treatment,
- TEAEs and maximum CTCAE grade / TEAEs related to study treatment and maximum CTCAE grade,
- TEAEs leading to death / TEAEs related to study treatment leading to death,
- Non-serious TEAE.

A patient with multiple occurrences of an AE will be counted only once in the AE category. SOCs will be sorted by descending order of frequency for the overall group, PTs will be sorted by descending order of frequency for the overall group within each SOC.

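### The protocol gives four different reporting periods for ALT ≥ 1.5 x baseline, and the SAP gives no source, derivation or period for this AESI, so its count may depend on which section a site followed

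*Protocol*

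**What the plan says.** Protocol 7.5.2.1 sets the surveillance rule: an ALT of at least 1.5 x baseline ("in any laboratory in charge of analysis) up to 9 months post-VTX-801 infusion should be reported to the Sponsor within 24 hours"), by entry into the trial database. Section 7.5.2.2 asks the investigator to enter the AE within 24 hours, and to discuss reactive steroids, when such a rise "is observed between Week 2 and Month 9 post-VTX-801 administration". Section 10.5.3 sends sites to 7.5.2 for a rise to 1.5 x "baseline between Week 4 and Month 6 post-VTX-801 administration occurs despite the immunosuppressive regimen".

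Section 9.6 lists the same threshold as an AESI under the lead-in "The AESIs for this study (defined at any timepoint in the study after VTX-801 administration) are", and adds that "AESIs are reportable to the designated Aixial DSPV group from the time of VTX-801 administration regardless of seriousness or causality". Section 9.3.2 requires any AESI meeting 9.6 to be "entered into the eCRF within 24 hours of first awareness", with no Month 9 limit. Section 8.1.11 says that reports of ALT at this threshold "will also be made available to Sponsor within 24 hours of the laboratory value being available"; it states no end date but refers back to 7.5.2.

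SAP 7.9.1 gives AESIs one row in the overview of treatment-emergent events: "Adverse events of special interest (AESI) / AESI related to study treatment". It ties related AEs, SAEs, fatal AEs and liver AEs to named eCRF fields. It does not do this for AESIs.

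**The concern.** One laboratory finding has four stated periods. Three of them sit in the text a site would consult when an ALT result comes back, and those three end at Month 9 or Month 6. Section 9.2.4 also says that abnormal laboratory values are not routinely to be entered as AEs. Its four exceptions (SAE criteria, discontinuation or interruption, medical intervention, clinical significance) do not include AESI status. The threshold is relative to baseline with no upper-limit-of-normal condition, so a value inside the normal range can qualify and easily be left out.

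Liver toxicity is a named product risk (Protocol 2.5.1), and safety is the primary objective. If sites read the sections differently, a late ALT rise could be in the laboratory data but missing from the AESI count. A fall in ALT AESIs after Month 9 could then not be told apart from a fall in reporting.

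**Working it through.** The plan states no figure for this point, so the check is a reading of the sections followed by a count.

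**1. Reporting periods side by side**

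| Protocol section | Period for ALT ≥ 1.5 x baseline | Action |
|---|---|---|
| 7.5.2.1 | up to 9 months | report to sponsor in 24 h, by database entry |
| 7.5.2.2 | Week 2 to Month 9 | enter AE in eCRF in 24 h; discuss steroids |
| 10.5.3 | Week 4 to Month 6 | refer to 7.5.2 |
| 8.1.11 | none stated; refers to 7.5.2 | laboratory report to sponsor in 24 h |
| 9.6 and 9.3.2 | any time after dosing | enter AESI in eCRF in 24 h |

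The first and last rows ask for nearly the same act. The clock differs: it starts when the value is available in 7.5.2.1 and at first awareness in 9.3.2. The protocol does not say how the two rules relate.

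**2. Scheduled ALT after Month 9** (Protocol Section 10 visit tables, escalation cohorts)

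- Through Week 36: V7 to V10 (4), V11 to V17 (7), V18 (1), V19 to V25 (7), two at Week 12, then V31, V33 to V38 and V39 (8). Total 4 + 7 + 1 + 7 + 2 + 8 = 29.
- Weeks 40, 44 and 52: 3. Years 2 to 5 (V47 to V56): 10. Total 29 + 3 + 10 = 42.
- Week 40 is borderline: it starts at 39 × 7 / 30.4375 = 8.97 months and ends at 40 × 7 / 30.4375 = 9.20 months. Week 44 starts at 43 × 7 / 30.4375 = 9.89 months.
- Five-year plan: 13 of 42 (31%) with Week 40, or 12 of 42 (29%) without it.
- SAP 5.1 visit table, which runs to Month 24: V44 to V50 = 7 with Week 40, or 6 without it.

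**3. Could another planned output recover a missed event?**

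- SAP 7.9.2 summarises continuous laboratory values by visit and lists them. It does not count patients reaching 1.5 x baseline.
- SAP Section 9 drops the laboratory shift tables.
- SAP 5.1 keeps unscheduled values out of summaries. It also averages repeats at starred visits; these all fall by Week 36, so averaging can blunt early rises but not late ones.
- The liver AE category in SAP 7.9.1 requires suspected DILI, a higher bar.

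A missed event would survive only as a raw value in the laboratory listing.

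**4. Size per patient.** SAP Section 9 reports four patients dosed, two per cohort. One missed patient is 1/4 = 25 percentage points overall and 1/2 = 50 within a cohort. The AESI row counts patients and pools all AESIs, so it moves by this much only if the missed rise is that patient's sole AESI.

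**The case against.** The strongest reply is that the protocol, read as a whole, already requires the report. Section 7.5.2.1 does not say that reporting ends at Month 9. It sits under mitigation of transaminase rises, and its window can be read as an operational alert inside a longer AESI duty. Sections 9.3.2 and 9.6 set that duty with no end date. Table 16 also captures all AEs to the one-year visit, and after that all but the incontrovertibly unrelated. This stands: a site that stopped at Month 9 would breach 9.3.2 and 9.6. A reader might infer that the protocol lets sites stop reporting at Month 9; the documents do not support that.

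Three other strong readings also fail:

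- That the SAP counts AESIs over all follow-up. SAP 7.9.1 gives a start (the day of dosing) and no end; the full period is only inferred from that silence.
- That late rises after a change of background therapy could be lost. SAP 4.1 records that withdrawal, adjustment and reinstatement did not occur.
- That most of the follow-up, (60 − 9)/60 = 85%, lies outside the window. This describes the five-year plan, not the reduced safety follow-up in SAP Section 3.

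It is also fair that four patients' ALT listings can be read by hand. That makes a late rise visible, but it does not correct the AESI row. Nor does the reply explain how a site should reconcile 7.5.2, 9.2.4 and 9.6.

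**Conclusion.** The inconsistency is real and worth correcting, but it is a risk of uneven reporting and not an instruction to stop. The duty stays open under 9.3.2 and 9.6. A site working from 7.5.2 and 9.2.4 could still omit a rise after Month 9, and the SAP has no rule to recover it. The exposure is 6 to 7 scheduled panels per patient on the SAP visit table, against 12 to 13 of 42 under the five-year plan.

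This assumes that patients had ALT measured at the scheduled visits after Month 9. The documents do not say how many of the four did. The interim analysis falls before one year after the last dosing, and follow-up is reduced. The 25 and 50 percentage points are the most that one missed patient can move the row. No late rise is known to have been missed.

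**What to change.** In the protocol, reconcile the reporting periods in 7.5.2.1, 7.5.2.2, 8.1.11 and 10.5.3 with 9.3.2 and 9.6, and name AESIs as an exception in 9.2.4. Two of these windows also govern the steroid pathway. The change should concern reporting only, and this point takes no position on any treatment window.

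In SAP 7.9.1, state the source and period for this AESI and add a derived flag:

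- Use all recorded ALT results, scheduled and unscheduled, each divided by the last pre-dose value from the same laboratory. This follows the baseline rule in SAP 5.3. Visit 2 (Day -7) is the last scheduled pre-dose panel and has both central and local results.
- Show central results as the main count and local results separately. Weeks 40 and 44 are scheduled as local panels, while the footnote to Protocol Table 10 reserves statistical analysis for central results.
- Reconcile the flag with site-reported AESIs, and show it before and after Month 9.

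The cost is a wording clarification across several protocol sections and one variable from data already collected. The downsides are a few more low-grade ALT events counted and a stated departure from the central-only rule for the local display. The final analysis, which supports the CSR addendum (SAP 8.1), is a natural place to apply it.
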